Given the potential severity of depression among those in the sample, some will express suicidal thoughts. Counsellors will be trained to implement a standardized protocol when patients report suicidal thoughts, including assessment of the severity of the ideation, intent and means for carrying out any intent for suicide; and activation of a plan to keep the patient safe. In order to maintain the scientific integrity of this human subject research project, and to protect the safety of its research participants, we will assemble a Data Safety Monitoring Board (DSMB) comprising members with appropriate clinical and technical expertise. The DSMB will have the responsibility of assuring that participants are not being exposed to unnecessary or unreasonable risks as a result of the pursuit of the study's scientific objectives. All data collected over the course of the trial—including from study participants and household members—will be stored on an encrypted, password protected server to which only research study staff (including clinical staff providing depression care) have access.

Availability of Data

For dissemination purposes, reporting results will be documented on ClinicalTrials.gov in accordance with NIH requirements. Information submitted will occur no later than 12

months after the primary completion date. Results produced by this investigation will be presented at conferences where applicable and published in a timely fashion. In the final year of the project, we will also host a conference and invite government officials to discuss findings in the broader context of Malawian policy initiatives. All final peer-reviewed manuscripts that arise from this proposal will be submitted to PubMed Central for open access. When applicable, deidentified analytic code and the associated datasets will be deposited in public repositories— including Harvard University’s Dataverse database: <https://dataverse.harvard.edu>.

DISCUSSION

This study will conduct a district-wide stepped-wedge cluster randomized trial to assess the effects of an evidence-based stepped care depression treatment model vs. usual care on depression symptom alleviation as well as quantifying improvements in physical health and household dynamics. While there is evidence of the deleterious effects of depression on mental health, this will be one of the first studies to quantify treatment benefits on physical health outcomes and household-level outcomes, and to incorporate these knock-on effects in cost-effectiveness estimates. We anticipate that by leveraging the existing infrastructure of the robust HIV care delivery system, the IC3 model and by quantifying these knock-on effects, expansion of depression care will be highly cost-effective and financially feasible for scale-up in Malawi.

Building on our research with task-shifted evidence-based depression care for HIV clients in Uganda, and our use of problem solving therapy (PST) and ADT in low-resource settings such as Rwanda and Haiti,^{98,99} this study is specifically designed to test a group-based

model of PM+ that WHO has advocated for broad scale-up. Moreover, the model focuses on an existing and growing cadre of counsellors throughout Malawi to deliver group-based PM+ and will measure fidelity to protocol execution, among other measures. Through close partnership with the Ministry of Health, in the final year of this project we intend to host a conference reviewing major findings of this work and to facilitate a discussion—including a technical expert panel—to outline potential strategies for wider scale-up.

TRIAL STATUS

This is Protocol version 1.0, dated February 25, 2021. Recruitment is anticipated to begin July 15, 2021 and complete on July 14, 2024.

LIST OF ABBREVIATIONS

- A1C: Hemoglobin A1C
- ADT: Antidepressant therapy
- ARSS: AIDS-related stigma scale
- ART: Antiretroviral therapy
- ARVs: Antiretrovirals
- BAS: Burden assessment scale
- CAC: Cluster autocorrelation coefficient
- CIDI: Composite International Diagnostic Interview
- DSMB: Data and safety monitoring board
- EQ-5D-5L: EuroQol 5 dimensions 5 levels
- HIV: Human immunodeficiency virus
- IAC: Individual autocorrelation coefficient
- IC3: Integrated Chronic Care Clinics

- IC3D: Integrated chronic care clinics – depression module
- ICC: Intraclass correlation coefficient
- ICER: Incremental cost-effectiveness ratio
- ISMI: Internalized stigma of mental illness scale
- ITT: Intention to treat
- LAMIC: Low- and middle-income country
- MCMC: Markov chain Monte Carlo
- MSPSS: Multidimensional scale of perceived social support
- NCD: Non-communicable disease
- NIMH: National Institute of Mental Health
- PHQ-2: Patient Health Questionnaire – 2-Item
- PHQ-9: Patient Health Questionnaire – 9-Item
- PIH: Partners In Health
- PM+: Problem Management Plus
- QALY: Quality-adjusted life year
- RCT: Randomized controlled trial
- SSRI: Serotonin selective reuptake inhibitor
- TB: Tuberculosis
- TCA: tricyclic antidepressant
- TDABC: Time-driven activity-based costing
- WHO: World Health Organization
- WHODAS: World Health Organization Disability Assessment Schedule

DECLARATIONS

Ethics approval and consent to participate

This study has received ethics approval from the RAND Human Subjects Protection Committee as well as the National Health Science Research Committee of Malawi. The authors

will receive verbal or written informed consent to participate in the study from all participants.

Consent for publication

Publication of findings will not include any identifiable details. A model consent form can be provided to individuals upon request.

Availability of data and materials

The authorship team will have access to the final trial dataset. All final peer-reviewed manuscripts that arise from this proposal will be submitted to PubMed Central for open access. When applicable, deidentified analytic code and the associated datasets will be deposited in public repositories—including Harvard University's Dataverse database:

<https://dataverse.harvard.edu>.

Competing interests

The authors declare they have no competing interests.

Funding

This study is funded by the National Institute of Mental Health (R01 MH117760). The funder had no role in the study design or implementation of activities, apart from ensuring compliance of ethics guidelines.

Authors' contributions

RKM and GW are the Principal Investigators; they conceived the study, led the proposal and protocol development. EW, EC, TR, WK, MC, and CK contributed to study design and to development of the proposal. SM was the lead trial methodologist. All authors read and approved the final manuscript. No professional writers were utilized to generate this manuscript.

Acknowledgements

The authorship team would like to thank the many members of the PIH/APZU family for making this project a reality. We would also like to acknowledge the ongoing engagement, support, and partnership of the Ministry of Health in Neno District as well as at the national level. Their vision to provide exceptional healthcare to meet the mental as well as physical needs of patients is a testament to the vision and commitment of these individuals.

REFERENCES

Automatic citation updates are disabled. To see the bibliography, click Refresh in the Zotero tab.

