Arm 5	Pre	Pre	Pre	Pre	Pre	Pre	Pre	Pre	Pre	Pre	Pre	Pre	Pre	Pre	Pre	Int	Int	Int	Post	Post	Post	Post	Post	Post	Post	Post	Post	Post	Post	Post

Legend: Pre-intervention (light green), Intervention (red), Post-intervention (light blue), 6-month follow-up (medium blue), 12-month follow-up (dark blue)

Footnote: Each arm represents 2-3 health clinics that have been randomized to that particular arm.

A schedule of trial activities is shown in Table 1. Within each cluster, we will use an open cohort design of individual participants who screen positive for potential depression. All attendees at each clinic will be screened at each time point and screen-positive patients will enter the cohort and be followed for the rest of the study—including after initiation of depression care at their site to assess how depression and depression alleviation relate to our primary (depression symptom alleviation; alleviation of functional impairment) and secondary

(HIV patients: viral load; hypertension patients: systolic blood pressure; diabetes patients: A1C or blood glucose levels; all patients: health utility index) outcomes, as well as processes of care (treatment uptake; adherence; perceived mental health stigma). Furthermore, prior to receipt of depression care, as well as six months later, one household member per participant will be interviewed in order to examine changes in their mental and physical health status. A cost-effectiveness analysis will be used to examine the incremental cost of integrated depression care (IC3D) over and above usual care within the IC3 framework.

Randomization, Allocation and Blinding

Health clinics will be randomly allocated to the five arms, the roll-out of which is spaced apart at 3-month intervals, with one exception: 13 potential combinations will be restricted from this algorithm, due to logistical considerations in the geographical layout of Neno District (note that over a quadrillion theoretical permutations are retained). This randomization will be executed by the project principal investigators using a random sequence generator in Stata 15.²⁹

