The Integrated Chronic Care Clinics Depression (IC3D) module draws from best evidence on collaborative care models for depression in low-resource settings.^{40,41} We will use a gold standard, stepped-care approach to offering psychological and pharmacologic treatment across all treatment facilities and clinics. Usual care will be augmented with evidence-based Problem Management Plus (PM+) through provision of manualized, group-based counseling sessions, and antidepressant therapy (ADT) for those with severe depression (or if PM+ is

declined), which is consistent with WHO mhGAP guidelines⁴² for use of ADT. The primary components of the depression care model are described below.

Psychoeducation and treatment selection: If eligible for treatment, the counsellor will inform the client of the availability of PM+ and ADT as treatment options, in addition to encouraging the client to access general supports—such as peer support groups—within Neno. Psychoeducation on depression, treatment course, possible side effects, and benefits of treatment will be provided. Clients will have the autonomy to select their preferred treatment, but the counsellor will encourage clients with moderate depression (PHQ-9 < 15) to consider group-based PM+ counseling given its established efficacy and absence of significant side effect concerns, while adults with moderate-to-severe and severe depression (PHQ-9 ≥ 15) will be encouraged to consider joint ADT and group-based PM+. If the client remains depressed after 12 weeks of receiving either depression treatment modality (as measured by PHQ-9 at quarterly visits), s/he will be offered to switch to or add the other form of treatment.

In the event an enrolled individual no longer meets criteria at treatment initiation, the individual will leave the cohort and not be eligible for treatment but will continue to be evaluated every three months for future eligibility. Given that screening, diagnosis and enrollment will occur at all facilities over the full trial period, we expect any reduction in patients enrolled in the cohort due to lagged treatment initiation will be offset by newly-identified individuals over this same period. This is consistent with an open cohort design for stepped-wedge trials.⁴³

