The data from the trial will be analyzed using a generalized linear mixed model framework, which is standard for stepped-wedge cluster designs.^{87,88} The patients participating form an open cohort with repeated measures, as it will be possible to link each patient taking a PHQ-9 screening and any subsequent exams over time. The models will be at the patient-level, nested within clinic-months and clinics. The primary outcomes are: (i) prevalence of depression; (ii) depression severity (PHQ-9 score) conditional on having depression; (iii) WHODAS score conditional on having depression; and (iv) utility score (0 to 1) from the EQ-5D-5L. The first outcome is a dichotomous event for if the patient has depression or not, while the remaining outcomes are treated as continuous. For the principal analysis of the trial, we used the “complete” stepped-wedge of data from months 1 to 18; long-term follow-up will constitute a secondary analysis.

We specify the following model for patient $i = 1, \dots, N$ in clinic $j = 1, \dots, J$ at time period $t = 1, \dots, T$:

$$y_{ijt} \sim F(g(\eta_{ijt}))$$

$$\eta_{ijt} = \mu + x'_{ijt}\beta + z'_{jt}\gamma + \delta D_{(i)jt} + \theta_i + \alpha_j + \phi_{jt} + \tau_t$$

where y_{ijt} is the outcome, $F(\cdot)$ is an appropriate likelihood and $g(\cdot)$ is a suitable link function, x_{ijt} and z_{jt} are respectively patient and clinic level covariates, τ_t are monthly fixed effects, and $\theta_i \sim N(0, \sigma_\theta^2)$, $\alpha_j \sim N(0, \sigma_\alpha^2)$, and $\phi_{jt} \sim N(0, \sigma_\phi^2)$ patient-, clinic-, and clinic-time random

effects term. We will take both intention to treat (ITT) and per protocol approaches. For the ITT analysis, the variable D_{jt} is an indicator equal to one if cluster j is in the intervention state at time t and zero otherwise, thus δ represents our estimated treatment effect. For per protocol analysis D_{ijt} will be a patient-level variable equal to one if the clinic was in the intervention state and the patient completed the treatment as defined above, and zero otherwise. For dichotomous outcomes, we will use a Bernoulli distribution with logistic link function, for continuous outcomes a normal distribution with identity link function. The same models will be used for secondary outcomes.

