The parameters of interest are δ_k , which are a (log) odds-ratio for the prevalence outcome and a mean absolute difference in score for the three individual-level outcomes. We will take both intention to treat (ITT) and per protocol approaches for the individual level outcomes. For the ITT analysis, the variable D_{jt} is an indicator equal to one if cluster j is in the intervention state at time t and zero otherwise. Thus, δ represents our estimated treatment effect. For the per protocol analysis, D_{ijt} will be a patient-level variable equal to one if the clinic was in the intervention state and the patient completed the treatment as defined above, and zero otherwise. As we describe below, we will use a randomisation test method to derive exact inferential statistics (p-values and confidence intervals) for the parameters of interest.

Outcomes 2-4 described above are only recorded for those who screen positive for depression at their scheduled visit. Thus, the data do not all cover the full patient population: data for outcomes 2 to 4 are a subset of those for outcome 1. Based on this, we anticipate the data to be normally distributed. However, we will test this assumption by examining QQ plots and conducting KS (Kolmogorov Smirnov) and SW (Shapiro Wilk) tests. In the event the normality assumption is violated, we will consider an alternative specification, such as a two-part semi-continuous model.

Statistical Inference

All models will be estimated separately using restricted maximum likelihood, using the R package lme4. We will report point estimates, confidence intervals, and p-values but not make any claims of "statistical significance", given recent strong arguments against doing so [2].

P-values will be based on the null hypotheses $H_0: \delta_k = 0$ versus the two-sided alternatives $H_1: \delta_k \neq 0$ in each of the models defined above. Given that there are multiple primary outcomes, we will adjust reported p-values for multiple testing using a cluster-based stepdown method, which provides an efficient means of controlling the family-wise error rate [18]. The full methodology is described elsewhere, but we describe it here briefly.

Let there be P hypotheses to be tested H_1, \dots, H_P with associated test statistics T_p . We let the ordered test statistics be:

$$T_{[1]} \geq T_{[2]} \geq \dots \geq T_{[P]}$$

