Outcomes 2-4 described above are only recorded for those who screen positive for depression at their scheduled visit as these instruments are not used for other patients in the trial. For each time period (quarterly), any patient eligible for screening (i.e. in the "denominator population") will have a value for recorded for Outcome 1 equal to one if they screen positive and meet the pre-defined criteria for entry into the depression care programme, or zero otherwise. The model is thus a "two-stage" type model with only those with defined depression contributing data from Outcomes 2-4 to the likelihood. Letting Y represent all the data, the log-Likelihood is therefore:

$$\begin{aligned} \log L(\theta|Y, \Phi) &= \log f(Y; \theta, \Phi) \\ &= \sum_{i=1}^n \left(1 - y_{ijk}^{(1)}\right) \log\left(1 - g_1\left(\eta_{ijt}^{(1)}\right)\right) \\ &\quad + y_{ijk}^{(1)} \left(\log\left(g_1\left(\eta_{ijt}^{(1)}\right)\right) + \log f_2\left(y_{ijt}^{(2)}; \theta, \Phi\right) + \log f_3\left(y_{ijt}^{(3)}; \theta, \Phi\right)\right) \\ &\quad + \log f_2\left(y_{ijt}^{(3)}; \theta, \Phi\right) + \log f_\phi(\Phi; \omega) \end{aligned}$$

where ω are the parameters of the joint distribution of random effects. The likelihood function for the parameters alone is determined by integrating out the random effects Φ and then maximising the resulting likelihood. Given the complexity of our model including non-linear effects, two-stage models, and multiple shared random effect terms, there exists no "out of the box" software that could reliably be used. Instead an alternative approach, such

as Monte Carlo Maximum Likelihood would be required. Given the technical complexity required, and any simulation-based testing that would be required to ensure any custom-built sampler was functioning correctly, we instead opted for a univariate methodology.

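### Patients who have recovered before treatment starts leave the cohort in the intervention state only, which biases cohort-based secondary outcomes (and EQ-5D under the Protocol's definition)

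*Protocol*

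**What the plan says.** Protocol, Study Design: "screen-positive patients will enter the cohort and be followed for the rest of the study", including after care begins at their site, so that the primary and secondary outcomes can be assessed. Recovery is not given as a reason to leave.

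Protocol, Treatment: IC3D (psychoeducation and treatment selection): where "an enrolled individual no longer meets criteria at treatment initiation, the individual will leave the cohort and not be eligible for treatment". Such a person "will continue to be evaluated every three months for future eligibility". The Protocol defends the rule by expecting that "any reduction in patients enrolled in the cohort due to lagged treatment initiation will be offset by newly-identified individuals over this same period", and calls this consistent with an open cohort.

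Protocol, Analysis of Intervention Effects: intention to treat is defined by the clinic's state in each period. Severity and WHODAS are conditional on having depression; the EQ-5D utility score carries no such condition. On the remaining outcomes: "The same models will be used for secondary outcomes".

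SAP, Individual-level outcomes: "Outcomes 2-4 described above are only recorded for those who screen positive for depression at their scheduled visit". The Appendix repeats this and adds the reason, "as these instruments are not used for other patients in the trial". Here EQ-5D utility is one of outcomes 2-4. Prevalence is a count per clinic and period among everyone screened.

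Neither document says how patients who leave under the Treatment: IC3D rule enter the intention-to-treat analysis.

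**The concern.** The Study Design and Treatment: IC3D rules cannot both hold for a patient who enrols while depressed and has recovered by the time care would start. The second rule acts only where care starts, so whether such a patient stays in the cohort depends on the clinic's randomised sequence. Take a patient who enrols in month 1 and has recovered by the end of month 3. In an Arm 1 clinic, which switches at month 4, that patient leaves. In an Arm 5 clinic, which switches at month 16, the same patient stays in the control-state cohort.

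Newly identified patients restore the headcount, but they are depressed when they enter and the people they replace were not. On any outcome measured in the whole cohort, control periods then include natural recoveries while intervention periods have lost those that occurred before treatment began. If recovered patients have better adherence or disease control, IC3D looks worse than it is and a real benefit could be masked.

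**Working it through.** **1. The plan's own figure.** 30 enrollees per facility x 14 facilities = 420, as stated. It reproduces, but it concerns numbers and does not test cohort composition.

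**2. Which outcomes depend on cohort membership?**

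| Outcome | Who supplies data | Touched by the exit rule? |
|---|---|---|
| Prevalence | All screened, clinic-period counts | No |
| PHQ-9 severity, WHODAS | Positive at that visit, either state (SAP) | About nil |
| EQ-5D utility | SAP: as above. Protocol analysis section: no condition | Only under the Protocol's definition |
| Viral load, systolic pressure, A1C/glucose, ART adherence, HIV staging | Cohort members, from routine care or records | Yes |

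The SAP ties its positive-visit restriction to the questionnaires, so it does not carry over to outcomes taken from routine care.

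**3. Size of the shift in cohort mix, with no treatment effect.**

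From the documents: 14 clinics in five arms of 2-3 (hence 3, 3, 3, 3, 2); six quarters (months 1-18); Arm 1 switches in quarter 2 and Arm 5 in quarter 6; ICC 0.05, CAC 0.80.

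Assumed: one unit of new entrants per quarter, all depressed; relapse q = 0.10 per quarter; remission p = 0.05 to 0.40 per quarter, the same in both states; 30 per clinic-quarter for weighting; the two-clinic arm last; removed patients do not return (letting relapsers back in would make the shift more negative).

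With D depressed and R remitted members:

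- R(t) = (1 - q)R(t-1) + pD(t-1)
- D(t) = (1 - p)D(t-1) + qR(t-1) + 1
- remitted share s = R/(R + D), with R set to 0 in the arm's switch quarter

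Example with p = 0.20:

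- Quarter 2, control clinic: R = 0.20, D = 0.80 + 1 = 1.80, s = 0.20/2.00 = 0.10. Arm 1, switching: s = 0/1.80 = 0.
- Quarter 3, control clinic: R = 0.9 x 0.20 + 0.2 x 1.80 = 0.54, D = 0.8 x 1.80 + 0.1 x 0.20 + 1 = 2.46, s = 0.54/3.00 = 0.18. Arm 2, switching: s = 0.

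The shares were fitted by generalised least squares as s = period effect + delta x (clinic in intervention state), with clinic and clinic-period covariance:

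| Quarterly remission | Spurious delta in remitted share |
|---|---|
| 5% | -0.06 |
| 10% | -0.11 |
| 20% | -0.20 |
| 30% | -0.28 |
| 40% | -0.34 |

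With IAC 0.80 added, the last three become -0.22, -0.30 and -0.37. Without the exit rule delta is 0 throughout.

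**4. Translation to an outcome.** Bias is roughly the shift times the remitted-minus-depressed difference. For utility under the Protocol's definition, with an assumed gap of 0.1 to 0.2: at 5% remission, -0.06 x 0.1 = -0.006; at 20%, -0.20 x 0.1 = -0.02; at 40%, -0.34 x 0.2 = -0.07. The documents give no such gap for the physical-health outcomes, so no figure is offered for them.

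**5. Does the rule matter under the SAP's recording restriction?** PHQ-9 was simulated with a true effect of zero (25 runs per scenario). Assumed: means 14.5 depressed and 6.0 recovered; recovery 10%, 20% and 30% per quarter; relapse 5%, 5% and 10%. Positive values count against IC3D.

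| Cohort rule | 10% | 20% | 30% |
|---|---|---|---|
| All enrolled kept and measured | +0.05 | +0.08 | +0.04 |
| Exit rule, recovered controls kept and measured | +1.36 | +2.35 | +3.15 |
| SAP restriction alone | +0.03 | +0.02 | +0.02 |
| SAP restriction plus exit rule | +0.03 | +0.02 | +0.02 |

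Monte Carlo standard errors are 0.04 to 0.06. The last two rows coincide because a patient removed for being negative would not have been recorded at that visit anyway, and counts again once positive. This takes the exit criterion and the recording criterion to be the same.

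**The case against.** The strongest reply is that the rule leaves the primary analysis as the SAP defines it alone. That stands. A recovered control-state patient supplies no PHQ-9, WHODAS or EQ-5D record either, and prevalence does not use the cohort. A reader might infer from the Study Design section that recovered controls stay in for every outcome, so that all primary estimates are biased; the SAP's recording restriction rules that out. Conditioning on current depression raises a separate question, not argued here.

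A reader might also infer that the intervention sample loses every spontaneous recovery. It does not. Only patients recovered before their own treatment initiation leave, later recoveries stay, and those removed can qualify again.

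It is also fair to say that the remitted share is not a trial outcome, that the remission rates are assumed, and that the effect is small at the low end.

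Two defences do not stand. An open cohort allows entry and exit, but it does not make exit that depends on exposure harmless. The complier-average analysis in the SAP addendum does not repair this, because its sample would be selected by the same rule.

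**Conclusion.** The concern holds for outcomes measured in the cohort whatever the current screen result: viral load, systolic pressure, A1C or glucose, ART adherence and HIV staging. It extends to EQ-5D only if the Protocol's unconditioned definition overrides the SAP's. For these, an exclusion that depends on outcome status and on randomised exposure breaks the intention-to-treat comparison.

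The direction is against IC3D, provided recovered patients do better on the outcome concerned. The documents do not fix the size. The shift of about -0.06 to -0.34 in remitted share rests on assumed remission of 5% to 40% and relapse of 10% per quarter, equal in both states. The utility figures rest in addition on an assumed gap and on the Protocol's definition, so they should not be read as an established bias in a primary outcome. Whatever the size, the Study Design and Treatment: IC3D rules conflict and the handling of removed patients is unstated.

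**What to change.** Leave the treatment-eligibility part of the Treatment: IC3D sentence as it is. Replace the cohort-exit part with: the individual remains in the study cohort, continues scheduled outcome follow-up, and is analysed under intention to treat according to the clinic's state.

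Add to the SAP: cohort membership is fixed at first enrolment, and no record is dropped because of status at treatment initiation.

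Reconcile the Protocol (Study Design, Treatment: IC3D, Overall health, Analysis of Intervention Effects) with the SAP (Analysis of Primary Outcomes, Individual-level outcomes, Appendix), so that one recording rule for WHODAS and EQ-5D applies to recovered patients in both states. This step is essential. If recovered patients were measured on the intervention side only, the bias would reverse: in the model of working step 3, the remitted share shifts by roughly +0.2, +0.3 and +0.4 in favour of IC3D at 20%, 30% and 40% remission.

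The cost is low. These patients are already evaluated every three months, and the physical-health outcomes come from routine care or records. Some extra questionnaires may be needed at existing visits in both states. The intention-to-treat effect will include enrolled patients who needed no treatment and may be smaller; the planned complier-average analysis speaks to the effect in those treated.
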